#### ii. Disclosure of HIV or other confidential information

Subjects will be protected against the risk and repercussions of accidental disclosure of HIV status in several ways. Confidentiality of study data is a priority and we will take many precautions to protect against the possibility of a breach of confidentiality. All research staff are aware of the importance of maintaining strict confidentiality and we have extensive experience dealing with sensitive mental health/alcohol use/HIV information. The following precautions will protect the privacy of participants and maintain confidentiality of research data: 1) All study staff will be well trained and will receive ongoing supervision in confidentiality and data security procedures, specifically in ethical conduct, confidentiality protection, mandated reporting, and other topics of human participant protection. 2) Privacy will be maintained by conducting all data collection activities in closed and private clinic rooms at CIDRZ/MoH clinics, in CIDRZ offices, and in MoH offices. Data will be transported daily in secure study vehicles from study sites to CIDRZ Headquarters where it will be uploaded to CIDRZ secure DHIS-2 server. 3) Each participant will be assigned a unique study ID number, and all data will be coded with ID numbers only and will not contain identifying information. The spreadsheet linking participant names, phone numbers, and addresses with ID numbers will be stored in a separate password protected document on a password-protected computer, to which only essential study staff will have access. Following the end of the study, the link will be destroyed such that all data are completely de-identified. 4) Paper-based data will be securely stored in separate locked file cabinets in locked offices. 5) Biological data (UETG) will be labeled only with an ID number and destroyed following recording of the test result. 6) Electronic data will be coded (no identifying information will be included) and stored on CIDRZ secure DHIS-2 encrypted server. Access to data storage areas and computers will be restricted. 7) Analysis will occur only on de-identified data and be presented in aggregate. 8) All participants will be encouraged to contact the local study direct, local investigators, or other staff to report any undesirable conduct associated with the study. These reports will be brought to the attention of the study director, local PIs and co-Is and the MPIs, and appropriate steps will be taken to solve the problems, including reporting to relevant ethical review boards.

- Describe the research burden for participants, including time, inconvenience, out of pocket costs, etc. Therapy sessions and assessments can be delivered either in the clinic or in a community location to minimize time or inconvenience burden on participants. While most study-related activities will occur during regular HIV care visits, participants may be required to come to the facility more often during the study, which incurs the cost of transportation and time.

- Describe how participant privacy will be protected during data collection if sensitive questions are included in interviews.

Data collection will be conducted in a private location within the HIV clinic where the participant is already receiving care or in a private room within a community location if the participant prefers. Data forms will only contain a study ID number and no personal identifying information of the participant. The only form linking the personal identifying information and the participant's ID number will be stored separately in a locked cabinet at CIDRZ headquarters and will only be accessible to required personnel. An electronic version of this form will be on a password-protected excel file that is also securely stored on CIDRZ DHIS-2 server. Outcomes data will be collected via ACASI, so an interviewer will not know the participant's responses to sensitive questions.

### **VIII. Direct Personal and Social Benefits:**

- Describe any potential direct benefits the study offers to participants ("payment" for participation is not a direct personal benefit).

Through participation in the research, participants will receive assessments that may benefit them by providing information about some of their problems, including alcohol use and mental health. Recipients of CETA will receive an evidence-based intervention that we already know positively impacts mental health problems.

- Describe potential societal benefits likely to derive from the research, including value of knowledge learned.

Capacity building: By training local interviewers in the assessment tools and peer educators in the two interventions, there is local clinical and research skill building. This has enormous benefit for them as individual professionals living in a low-resource country.

Scientific Field: We anticipate that this study will generate substantial indirect benefits to the participants as it will provide urgently needed answers to what may be effective interventions for reducing hazardous alcohol use and comorbid mental health problems.

Policy: A core principle of this research is that key stakeholders, including policymakers such as the Zambian Ministry of Health, will be involved in the study. Policy makers will be invited to the workshops and relevant meetings, and included on relevant communications, to share the research data for improving and integrating mental health services. Their involvement will serve as a compass for the work of this study, and allow real-time policy influence.

### **IX. Payment:**

- Describe the form, amount, and schedule of payment to participants. Reimbursement for travel or other expenses is not "payment," and if the study will reimburse, explain.

We recognize that additional time will be needed to complete study activities; therefore, we will provide reimbursement for travel to all study visits (screening visit, assessments and therapy sessions). The amount of this reimbursement will be 20 Zambian Kwacha, approximately \$2, which is the cost of round-trip bus fare (the usual mode of transport for clients to reach the clinics).

- Include the possible total remuneration and any consequences for not completing all phases of the research.

Participants are not being paid to participate in the study. There will be no consequences to the participants for not completing all phases of the research.

### **X. Study Management:**

#### **A. Oversight Plan:**

- Describe how the study will be managed.

A multiple PD/PI (MPI) approach will be used in the proposed study. Drs. [name] (based at CIDRZ/UAB) and [name] (based at JHU) are Early Stage Investigators (ESI) who have complimentary areas of expertise, were both responsible for project conceptualization and development, and will share responsibilities for overall scientific direction and oversight of the project. We are confident based on the extensive JHU-CIDRZ collaborative history working in Zambia and ongoing meetings and joint involvement with the development of the study idea and design, that we will be able to function together as a leadership team and that the benefits of a joint leadership approach will be evidenced through the strength of the study implementation and impact on policy and services. The MPIs will both have ultimate shared oversight for the operation of the research.

Three senior investigators were deliberately selected as Co-I to support the MPIs: (1) [name], a clinical psychologist, developer of CETA, and co-founder of the Applied Mental Health Research Group at JHU; (2) [name], an NIAAA-funded HIV clinical epidemiologist specializing in the treatment of alcohol use disorders; and (3) [name], a Social Scientist with >20 years of experience in design and evaluation of large health programs in Africa and Asia. Each Co-I has vast experience as PIs and are current collaborators with both Drs. [name] and [name] on active projects in Zambia.

The MPIs will be in constant communication by email (daily), phone (at least weekly; more as needed), and in-person (quarterly trips to Zambia by [name] funded through this and other projects). MPIs will be in constant communication with the Zambia-based team, including two conference calls per week (one full-team call; one for the data M&E team) to ensure ethical, scientifically sound, and productive implementation of the study.

- What are the qualifications of study personnel managing the project?

In addition to the PI's, investigators include [name] as well as [name] [name], a licensed clinical social worker, who has over a decade of clinical and research experience in Zambia and will lead along with [name] all CETA trainings and supervision. Finally, the field activities will be monitored by [name] who has over a decade of program and research management in Zambia, including as study director of our team's recently completed CETA trial.

- How will personnel involved with the data collection and analysis be trained in human subjects research protections? (Use the JHSPH Ethics Field Training Guide available on the JHSPH IRB website: [www.jhsph.edu/irb](http://www.jhsph.edu/irb).)

All personnel involved in human subjects research will be trained with the JHSPH Ethics Field Training Guide, the NIH human subjects modules. All will be certified before they are allowed to be involved in data collection or human subjects activities.

- If the PI will not personally be on-site throughout the data collection process, provide details about PI site visits, the supervision over consent and data collection, and the communication plan between the PI and study team.

[name] will be on-site regularly throughout the data collection process. [name] will be in contact with the team daily by email and twice weekly by conference call. [name] will make at least annual trips to Zambia.

#### B. **Recordkeeping:**

Describe how you plan to ensure that the study team follows the protocol and properly records and stores study data collection forms, IRB regulatory correspondence, and other study documentation. For assistance, contact [[contact]](mailto:[contact]).

Recordkeeping will be a core component of the weekly full team teleconferences. The study director based in Zambia will maintain a study spreadsheet to monitor that all study documentation, IRB regulatory correspondence, and other study documentation are organized and up to date.

#### C. **Safety Monitoring:**

1. Describe how participant safety will be monitored as the study progresses, by whom, and how often. Will there be a medical monitor on site? If yes, who will serve in that role?

Participant safety is monitored throughout the study by the clinical team, led by Co-I's [name], [name], and [name]. We will also convene a DSMB.

2. If a Data Safety Monitoring Board (DSMB), or equivalent will be established, describe the following:

- a. The DSMB membership, affiliation and expertise.

The 3 member DSMB will include individuals from CIDRZ, UAB and JHU faculty including an HIV expert, a statistician, an expert in conducting MH research in low-resource settings.

- b. The charge or charter to the DSMB.

The DSMB will assist the study in monitoring adverse events. The DSMB will meet as needed for the duration of the project. We will circulate to all DSMB members study protocols including formal procedures for reporting and tracking all adverse reactions to the NIH and IRBs; tracking progress in the study; and identifying any need for premature termination of the protocol. The DSMB will provide feedback to the PIs on these draft protocols. We will prepare progress reports to the DSMB every six months on concerning enrollment, attrition, and adverse events.

The DSMB will review these progress reports and respond with concerns to the MPis. Conference calls with the DSMB will be conducted on a schedule determined at the first DSMB meeting . Final reports approved by the DSMB will be generated.

- c. Plans for providing DSMB reports to the IRB.

All DSMB reports will be forwarded to the IRB within 30 days of the report being finalized.

- d. Describe plans for interim analysis and stopping rules, if any.

There are no plans for interim analyses.

**D. Reporting Unanticipated Problems/Adverse Events (AEs) to the IRB (all studies must complete this section):**

Describe your plan for reporting to the IRB and (if applicable) to the sponsor. Include your plan for government-mandated reporting of abuse or illegal activity.

Reportable Events

*Adverse Events.* The PI will be responsible for oversight of potential adverse events. An adverse event (AE) is any untoward medical occurrence in a subject during participation in the study. We anticipate two potential types of AEs that could be directly related to study participation. These include distress experienced with regard to research participation and breach of confidentiality and privacy. With regard to both matters, we have protocols in place that include conferring with the PI or a project mental health provider and appropriate safeguards to reduce risk of breach of confidentiality and privacy. Additional potential AEs are not likely, however we anticipate that AEs related to suicidal ideation and/or intent, homicidal ideation and/or intent, clinical worsening necessitating a higher level of care, and neglect/abuse may come to the attention of research staff during the consenting and recording process and during provision of care.

*Classification and Documentation of Adverse Events.* AEs will be classified by severity (mild, moderate, or severe) depending on the intensity of the event on the patient. An AE will be “mild” if it does not have a major impact on the patient, “moderate” if it causes some minor inconvenience, and “severe” if it causes a substantial disruption to the patient’s well-being. A severe AE is distinct from a serious adverse event (SAE), which is any AE that results in death, a life-threatening event, inpatient hospitalization, disability, congenital anomaly or birth defect, and/or an important medical event based upon appropriate medical judgment. AE’s and SAE’s will also be classified according to the likelihood that they are related to the study intervention. They will be labeled definitely unrelated, definitely related, probably related, or possibly related to the study processes. We will also collect unanticipated problems involving risks to subjects or others (UPIRSOs), protocol violations, and instances of non-compliance.

*Timeline for reporting.* We will provide bi-annual reports to the DSMB. We will use the following procedures in the event of an AE, SAE, UPIRSO, protocol violation, and instance of non-compliance. In the case of any of these instances, the research team will alert the PIs immediately (same business day). Subsequently, the PIs will submit a report within 10 working days (with one exception) of events that meet the definition of an unanticipated problem involving risks to subjects or others. The exception is if the SAE involved death and indicates that participants or others are at increased risk of harm, the PI will be required to submit a report to the DSMB within 3 days. Reports will be submitted electronically to the DSMB chair. The DSMB representative, when necessary in conjunction with the full DSMB, review reports and decide whether the event meets the definition of an unanticipated problem increasing risks to subjects or others. Events that meet these criteria will be considered unanticipated problems involving risks to participants or others, will be reviewed by the convened

DSMB. We will also notify the IRB within 3 days of unanticipated AEs related to the study and of any deaths using the adverse event reporting form. All adverse events will also be included in annual reports to the IRB.

NOTE: The IRB does not require PROMPT reporting of all AEs, only those that are **unanticipated, pose risk of harm to participants or others, and are related to the study**. Anticipated AEs may be reported with the Progress Report.

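### An SAE as such has no dated route to the DSMB: prompt reports cover only events already taken to be unanticipated problems, which is the question the DSMB is meant to decide

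*Combined protocol and SAP*

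**What the plan says.** Section X.D, Timeline for reporting, opens broadly: "We will use the following procedures in the event of an AE, SAE, UPIRSO, protocol violation, and instance of non-compliance". The first step, a same-day alert to the PIs, covers all of these. The next step is narrower: "the PIs will submit a report within 10 working days (with one exception) of events that meet the definition of an unanticipated problem". The single exception is a 3-day report to the DSMB for an SAE that involved death and that also points to increased risk of harm for participants or others. Reports are sent electronically to the DSMB chair. The DSMB representative, with the full board where necessary, is then to review them and "decide whether the event meets the definition of an unanticipated problem increasing risks to subjects or others".

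The IRB has a separate rule: "We will also notify the IRB within 3 days of unanticipated AEs related to the study and of any deaths".

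Routine reporting to the DSMB is in Section X.C: "We will prepare progress reports to the DSMB every six months on concerning enrollment, attrition, and adverse events". Section X.D repeats it: "We will provide bi-annual reports to the DSMB".

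Earlier in Section X.D, the definition of an SAE includes death and inpatient hospitalisation. The same section says that further AEs are not likely, but adds that "we anticipate that AEs related to suicidal ideation and/or intent, homicidal ideation and/or intent, clinical worsening necessitating a higher level of care" may come to the notice of research staff.

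**The concern.** Taken in order, the steps are circular. A report is released because the event meets the unanticipated-problem definition, and the board that receives it is then asked whether the event meets that definition. The DSMB can overturn a yes. It has no prompt sight of a no.

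There is also a gap. Seriousness alone does not trigger a DSMB report, because the trigger is being unanticipated. The randomised population is selected for moderate-to-severe AUD, depression, trauma symptoms or other substance use. The serious events most readily foreseen in it are the ones most easily classed as anticipated, and so left for the periodic report.

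Finally, the two oversight bodies are treated differently. The IRB hears of every death within 3 days, while the DSMB does so only if the death also indicates increased risk.

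What is at stake is the timeliness of safety oversight. No estimate, endpoint or analysis is affected. Section X.C asks the DSMB to assist in monitoring adverse events, plans no interim analysis and states no stopping rule. Individual event reports are therefore the only prompt signal that the text obliges anyone to send it.

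**Working it through.** The plan gives no calculated figure to reproduce. The check sets out the route for each type of event and then converts the limits to days.

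**Step 1: routes as written (Sections X.C and X.D).**

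| Event | To the DSMB | To the IRB |
|---|---|---|
| Death that indicates increased risk | 3 days | 3 days |
| Event meeting the unanticipated-problem definition | 10 working days | 3 days if an unanticipated AE related to the study |
| SAE classed as anticipated, not fatal | six-monthly report | annual report |
| Death judged neither to indicate increased risk nor to be an unanticipated problem | six-monthly report | 3 days |

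Two readings enter this table. The 10-working-day sentence names no recipient; the DSMB follows from the later sentence that reports go to its chair. Bi-annual is read as twice a year, because Section X.C says every six months.

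**Step 2: who applies the definition first.** Between the same-day alert and the submission, the text mentions only the PIs. That the PIs make the first classification is therefore an inference, though a close one. The DSMB's decision comes after submission.

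**Step 3: can an SAE be classed as anticipated?** Section X.D foresees worsening that calls for more intensive care. Section V lists psychosis needing hospitalisation as a reason for removal and names a hospital with inpatient psychiatric services for referral. An inpatient admission is an SAE by definition. An admission that follows foreseen worsening could thus be both serious and classed as anticipated.

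**Step 4: longest scheduled waits.**

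- 10 working days, with no public holidays = 14 calendar days.
- Six months = 365.25 / 2 = 182.6, about 183 days.
- Mean wait, if events fall evenly between reports = 182.6 / 2 = 91.3, about 91 days.
- Longest wait against the 10-working-day limit: 182.6 / 14 = 13.0, about 13 times.
- Longest wait against the 3-day limit: 182.6 / 3 = 60.9, about 61 times.

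**Step 5: against a participant's time in the study.** Section V allows up to one month to start CETA and then 6 to 12 weeks of weekly sessions. With about 4 weeks to start and no missed sessions, the longest course ends about 4 + 12 = 16 weeks after enrolment. Participation lasts about six months. An SAE that occurs just after one report could therefore first reach the DSMB after that participant's treatment has ended.

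**The case against.** The best defence is that this is an ordinary two-step process: the PIs forward suspected unanticipated problems and the DSMB confirms them. The procedure opens by naming AEs and SAEs, and nothing says that the PIs' view is final. This may well be the intention, and it would remove the circularity. But the submission sentence covers events that meet the definition, not suspected ones. Even on the generous reading, an SAE that nobody suspects of being an unanticipated problem still has no dated route.

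Secondly, the DSMB is not confined to the six-monthly report. Under Section X.C it meets as needed, sets its own call schedule, and comments on circulated procedures for reporting and tracking adverse reactions. Those procedures are not in the documents and might route SAEs directly. This stands as a limit on the finding: six months is the longest scheduled wait, not a blackout. But no passage requires earlier notice, and a board cannot call a meeting about an event of which it has not been told.

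Thirdly, Section VII provides weekly suicide and homicide risk questions in both randomised arms, home visits for BI-arm participants who do not respond to the phone contact, and on-call clinicians. These protect the individual. They do not inform the DSMB.

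Fourthly, the IRB template's note lets anticipated AEs wait for the Progress Report. That sets what the IRB requires, not what the DSMB should receive.

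Some stronger readings are tempting but not supported:

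- A reader might infer that the protocol declares psychiatric hospitalisation to be anticipated. It does not. The list in Section X.D does not name hospitalisation, and an admission judged unanticipated in nature or severity would still take the 10-working-day route.
- A reader might infer that deaths can go unreported for months. Every death reaches the IRB within 3 days, and one that meets the unanticipated-problem definition reaches the DSMB within 10 working days. Only the remainder can wait, and only for the DSMB.
- A reader might see several rules in outright conflict. Different thresholds for the DSMB and the IRB can both be followed. What the text contains is one circularity, one gap and one mismatch.

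**Conclusion.** The point holds for reporting to the DSMB. As written, the DSMB is asked to rule on a question that has already been used to decide what it is sent, and seriousness alone does not trigger a dated report to it. An SAE classed as anticipated, or a death judged neither to indicate increased risk nor to be an unanticipated problem, can wait up to about 183 days (about 91 on average) for the scheduled report.

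This rests on four assumptions: the PIs make the first classification; bi-annual means every six months; events fall evenly between reports (for the average only); and the circulated reporting procedures, which are not in the documents, do not already close the gap. How many events would be affected cannot be estimated from the documents. Section VII expects harms to be infrequent and minor, so the number should be small. This is a cheap improvement, not a flaw in the trial's inference.

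**What to change.** In Section X.D, Timeline for reporting:

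- Send every SAE to the DSMB chair within the 10 working days already in the text, regardless of expectedness or judged relatedness.
- Send every death to the DSMB within the 3 days already used for the IRB, without the added condition of increased risk.
- State that the DSMB makes the unanticipated-problem decision after it receives these reports, and name the DSMB chair as recipient in the submission sentence.

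No new time limit is introduced and the six-monthly report stays as it is. The cost is a protocol wording change and a few extra short reports for the PIs to write and the DSMB to read.
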